Study Protocol

**Efficacy and Safety of Prophylactic
Treatment for *Pneumocystis Jirovecii*
Pneumonia (PJP) in Patients with
Autoimmune Inflammatory Rheumatic
Disease (AIIRD)**

Version date: 2024.07.04

Background

Pneumocystis jirovecii pneumonia (PJP) is an opportunistic infection that occurs in immunocompromised patients. The typical clinical symptoms include fever, cough, and dyspnea, with a rapid onset and progression to hypoxemia and even respiratory failure. PJP can be divided into HIV-associated PJP and non-HIV PJP [1-2]. In recent years, with the increasing use of iatrogenic immunosuppressants, the incidence of PJP in non-HIV patients has risen, particularly among patients with autoimmune inflammatory rheumatic diseases (AIIRD), such as systemic lupus erythematosus, rheumatoid arthritis, inflammatory myopathies, and systemic vasculitis [3]. The incidence of PJP in AIIRD patients ranges from 0.7% to 2%, significantly higher than in the general population [4]. In addition, AIIRD patients with PJP are prone to progress to respiratory failure, with severe symptoms, poor prognosis and high mortality. Early identification and prophylactic treatment of PJP could improve outcomes and reduce mortality [5].

Currently, identifying PJP in AIIRD patients is challenging due to overlapping clinical features, such as fever and lymphopenia, and the reduced detection rates of Pneumocystis in respiratory specimens due to immunosuppressant use. Early warning based on serological markers offers a new approach for identifying PJP in AIIRD patients [6-8]. Although there are guidelines for preventing PJP in HIV patients, hematologic malignancies, and solid organ transplant recipients [9-10], no consensus guidelines exist for AIIRD patients on immunosuppressive therapy. More clinical evidence is needed to develop evidence-based clinical guidelines for prophylactic treatment of PJP in AIIRD patients.

This prospective controlled study will use machine learning and other information technologies to analyze clinical data from AIIRD patients. By fitting early clinical indicators (e.g., symptoms, laboratory results) with PJP infection and outcomes, combined with our center's predictive model (combination factor 1 = IgA – IgM × 2.072/1.411) and international consensus and expert recommendations on PJP prophylaxis [11-17], we aim to establish new screening criteria for high-risk populations, and stratified analysis was performed based on risk factors. We'll assess the efficacy

and safety of prophylactic treatment (TMP/SMZ) for PJP in AIIRD patients, explore the AIIRD populations that benefit the most from prophylactic treatment and evaluate the benefit-risk ratio of prophylactic treatment in AIIRD patients, aiming to achieve early identification and guidance for prophylactic treatment, ultimately reducing PJP incidence and improving outcomes in AIIRD patients.

Objectives

1. Develop and validate a predictive model for PJP infection risk in AIIRD patients to facilitate risk stratification, enhanced monitoring, and early prophylactic treatment.
2. Investigate the impact of prophylactic treatment on the incidence and outcomes of PJP in AIIRD patients, evaluating the efficacy, safety, and benefit-risk ratio of prophylactic treatment.

Study design

This study will prospectively collect peripheral blood, respiratory specimens, and clinical data from AIIRD patients, analyze the biological data, establish clinical prediction models, identify high-risk PJP populations among AIIRD patients and administer prophylactic trimethoprim-sulfamethoxazole (TMP/SMZ) treatment. The efficacy and clinical utility of the PJP infection risk prediction model will be validated, and the impact of prophylactic anti-PJP treatment on incidence and outcomes will be explored.

Selection of AIIRD patients

1. Inclusion criteria

- a) Diagnosed with AIIRD according to international classification criteria and receiving corticosteroid or immunosuppressant therapy;
- b) No prior standard PJP treatment, including first-line TMP/SMZ or other

second-line treatments;

- c) Age \geq 18 years;
- d) Informed consent signed for biological sample collection.

2. Exclusion criteria

- a) Significant health issues, including (but not limited to) the following: Patients with severe liver injury (elevated serum aminotransferase (ALT, AST), more than 5 times the normal value), severe renal insufficiency (GFR < 30mL/min or Scr > 445umol/L), severe myelosuppression (Hb < 65g/L, PLT < 25 \times 10⁹/L or neutrophil < 0.5 x 10⁹/L);
- b) Screening of known when infected with human immunodeficiency virus (HIV), over the past five years with lymphoid tissue proliferative disease or any organ system malignant tumor medical history, history of solid organ transplant patients;
- c) History of sulfonamide allergy or folate deficiency-related megaloblastic anemia;
- d) Pregnant and lactating women;
- e) Any medical or psychiatric condition that the investigator believes would prevent the trial participant from adhering to or completing the study according to the protocol;
- f) Patient refused to comply with the requirements of this study to complete the work.

Sample size estimation

It is expected to prospectively collect a total of 800 patients diagnosed with AIIRD in our hospital. Based on the previous literature and the experience data of our center, there were large differences in some tested indicators in some subgroups. Because involved in machine learning, the required number of samples roughly follows the http://blog.csdn.net/uestc_c2_403/article/details/72859021 url provided by the algorithm, which is about 10 times the number of dimensions + 1. Prospective data expected into the analysis of the parameters/index for 70. Considering that about 10-20% of patients may have missing data in real-world practice, the final sample size

for prospective collection was $70*1.2*10 \approx 800$.

Study process

1. Enrollment criteria and patient recruitment

a) Define enrollment criteria and recruit eligible AIIRD patients.

b) Explain the study purpose and obtain written informed consent.

2. Construct a clinical prediction model and recognize PJP high-risk patients

a) The prediction model was established by combining the developed prediction model (combination factor 1= IgA-IgM \times 2.072/1.411) with clinically recognized risk factors (including long-term use of high-dose corticosteroids, combination of immunosuppressants, and pulmonary diseases).

b) According above criteria, AIIRD patients with high risk or low risk of PJP are recognized.

3. Grouping and Experimental Intervention

a) Prospectively, we group AIIRD patients into high-risk and low-risk based on the prediction model, and they are further divided into 4 groups according to the intention-to-treat principle: high-risk group 1 (Patients intend to treat with prophylactic TMP/SMZ), high-risk group 2 (Patients intend to treat without prophylactic TMP/SMZ), low-risk group 1 (Patients intend to treat with prophylactic TMP/SMZ), low-risk group 2 (Patients intend to treat without prophylactic TMP/SMZ).

c) Trimethoprim-sulfamethoxazole intervention regimen: TMP/SMZ 480mg po qd (one tablet per day, oral); Treatment time: routine ≥ 28 days (according to the needs of the patient's condition, as well as the patient's tolerance to the drug and the willingness to treat, the clinician will adjust the time).

4. Follow-up and data collection

a) Establish a long-term follow-up to collect each clinical data on a regular basis.

Study visits were set at baseline, 6 and 12 months after the initiation of treatment. The

end points of follow-up were PJP infection, occurrence of serious side effects, death, loss to follow-up, end of follow-up, or withdrawal from the study. Main outcome indicator is pneumocystis infection incidence, and secondary indicators include TMP/SMZ related adverse events, PJP related mortality, other prognostic indicators and parameters of the respiratory system.

5. Statistics and data analysis

- a) Using difference test statistical analysis methods such as comparing two main outcome indexes between the groups of patients. Possible confounding factors, such as age, gender, and baseline conditions, were considered in the analysis, and covariates were adjusted if necessary.
- b) Statistical analysis methods (such as ROC curve, calibration plot, DCA curve, etc.) were used to evaluate the prediction model performance and visual display (Nomogram, etc.).
- c) Stratified according to risk factors, the absolute risk difference of PJP between the control and prevention groups was calculated, and the NNT was calculated based on the risk difference. The bootstrap method is used to estimate NNT and NNH 95% confidence interval (95% CI), for different people to undergo preventive SMZ/TMP risk-benefit assessments.

Possible risks and preventive measures

- a) Possible risks: (1) When peripheral blood samples are obtained from patients, some patients may have dizziness and other symptoms due to their physical weakness. (2) When obtaining induced sputum or bronchoalveolar lavage fluid from patients, some patients may have the risk of bronchospasm and asthma induction because they cannot tolerate it. (3) Adverse reactions of TMP/SMZ (such as rash, fever, purpura, nausea and vomiting, leukopenia, elevated transaminase, etc.) occurred during the treatment.
- b) Preventive measures: (1) Professional medical staff should take care of the blood collection place, assess whether the patient's current health status is suitable for

additional blood collection, and pay close attention to the patient's status during blood collection. The corresponding first aid drugs are stored at the blood collection site for a long time. (2) The respiratory specimen collection place will be attended by professional medical staff, who assessed whether the patient's current health status is suitable for respiratory specimen collection, and pay close attention to the patient's status during the collection process. The corresponding first aid drugs are stored at the collection place for a long time. (3) Follow up the patients' symptoms and signs regularly, and ask them to check the complete blood count, liver and kidney function, and electrolytes regularly. The TMP/SMZ should be stopped at the first appearance of rash or any signs of adverse reactions, and the adverse reactions should be treated with symptomatic treatment (such as anti-allergic, kidney protective, liver protective drugs; If is showing signs of bone marrow suppression, should be given to patients every day leucovorin 5-15 mg, until the hematopoietic function returned to normal, if necessary, can be used to promote red, white needle and boost platelet hormone therapy).

Reference

- [2] Sepkowitz K A. Opportunistic infections in patients with and patients without acquired immunodeficiency syndrome[J]. *Clinical infectious diseases*, 2002, 34(8): 1098-1107.

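### The 10-patients-per-dimension rule does not show that 800 is enough to develop a new PJP model from 70 indicators: the protocol's own incidence implies only about 6–16 cases

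*Protocol*

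**What the plan says.** The Sample size estimation section rests the total on one argument: "Because involved in machine learning, the required number of samples roughly follows the" algorithm found at a web address, "which is about 10 times the number of dimensions + 1. Prospective data expected into the analysis of the parameters/index for 70". It then allows for 10–20% of patients with missing data through a factor of 1.2 and arrives at about 800. Neither a PJP incidence nor an expected number of cases enters.

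The Background gives the incidence: "The incidence of PJP in AIIRD patients ranges from 0.7% to 2%, significantly higher than in the general population". It also sets out the modelling plan. "By fitting early clinical indicators (e.g., symptoms, laboratory results) with PJP infection and outcomes", together with the centre's existing predictive formula and published recommendations, "we aim to establish new screening criteria for high-risk populations". Objective 1 begins: "Develop and validate a predictive model for PJP infection risk in AIIRD patients".

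Study process, item 2a, describes a smaller model: the existing IgA/IgM formula combined with clinically recognised risk factors, of which three are named. Item 3a uses the prediction model to form the high-risk and low-risk groups.

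**The concern.** A rule of so many patients per dimension takes no account of how rare the outcome is. When almost every patient is a non-case, adding non-cases tells the model very little about what distinguishes a case, and the case count is the limit. The protocol gives a low incidence in one section and a sample-size argument that ignores it in another.

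At stake is Objective 1. A reader would take from the sample-size section that 800 has been shown to be enough for machine learning on 70 indicators. New high-risk criteria drawn from a handful of cases may perform much worse in new patients than in the data that produced them, and the protocol means such criteria to guide early identification and prophylaxis. Correcting for optimism would reveal that loss but could not repair it.

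**Working it through.** **Inputs.** From Sample size estimation: N = 800, 70 parameters/indexes, about 10 patients per dimension, 10–20% missing data, factor 1.2. From the Background: incidence 0.7–2%, with no time window. Incidences of 5% and 10% are my assumptions, added because all enrolled patients are on corticosteroids or immunosuppressants.

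**The plan's own figure.** 70 × 1.2 × 10 = 840, not 800. The rule without allowance gives 10 × 70 = 700 or 10 × 71 = 710. Since 800/700 = 1.14 and 1 − 710/800 = 11%, 800 fits the rule at about 11–14% missing. That lies within the stated 10–20%, but it is not what the factor 1.2 gives. This is a side note.

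**Expected cases = N × incidence; cases per indicator = cases/70.**

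| Incidence | Cases in 800 | Per indicator |
|---|---|---|
| 0.7% | 5.6 (binomial 95% range 2–11) | 0.08 |
| 2% | 16 (9–24) | 0.23 |
| 5% (assumed) | 40 | 0.57 |
| 10% (assumed) | 80 | 1.14 |

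- With 10–20% of patients lost to missing data, N is 720–640: from 640 × 0.007 = 4.5 to 720 × 0.02 = 14.4 cases.
- If half the patients also received prophylaxis that cut risk by 50–90% (assumed), 800 patients with no losses would give 400p + 400p(1 − r), with p the incidence and r the risk reduction: 3.1–4.2 cases at 0.7% and 8.8–12 at 2%.
- Even one case per indicator in 800 would need an incidence of 70/800 = 8.75%, over four times the protocol's upper figure. At the stated incidence it would take 70/0.02 = 3,500 to 70/0.007 = 10,000 patients.

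**What few cases do to a model.** This is a stylised illustration, not a projection: 800 patients, 70 independent normal variables of which 4 carry equal signal, a linear discriminant, and several hundred runs per setting. The AUC in new patients is computed exactly from the fitted weights. Means for 6 / 16 / 40 / 80 cases:

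| Model | Attainable AUC 0.75 | Attainable AUC 0.85 |
|---|---|---|
| All 70 fitted | 0.57 / 0.60 / 0.65 / 0.67 | 0.65 / 0.71 / 0.77 / 0.80 |
| Best 5 of 70 selected | 0.56 / 0.61 / 0.69 / 0.73 | 0.66 / 0.77 / 0.83 / 0.84 |
| The right 4, pre-specified | 0.70 / 0.73 / 0.74 / 0.74 | 0.82 / 0.84 / 0.85 / 0.85 |

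At attainable AUC 0.75, the apparent AUC of the all-70 model in its own data is about 0.996 with 6 cases and 0.957 with 16.

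**Precision for evaluating one fixed score.** With A the AUC, the Hanley–McNeil standard errors (non-cases = 800 − cases) are 0.116 (6 cases) and 0.071 (16) at A = 0.75, and 0.084 and 0.052 at A = 0.90. A symmetric interval fails here: 0.90 + 1.96 × 0.084 = 1.06. On the logit scale, logit(A) ± 1.96 × SE/[A(1 − A)], back-transformed, gives 95% intervals of 0.47–0.91 (6 cases) and 0.59–0.86 (16) at A = 0.75, and 0.59–0.98 and 0.74–0.97 at A = 0.90.

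**The case against.** **The protocol does not say that 70 predictors enter one model.** A reader might infer that it does. The text says only that 70 parameters enter the analysis, and the modelling sentence in the Background goes on to bring in the centre's formula and expert recommendations. This stands, and cases per indicator depends on the reading. But the section equates the 70 with the rule's dimensions and sizes the machine learning on them. If only the small model is meant, the 70-based argument justifies something else and still has to go.

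**The incidence may not apply.** The Background figure is for AIIRD patients in general and has no time window. The cohort consists of hospital patients "Diagnosed with AIIRD according to international classification criteria and receiving corticosteroid or immunosuppressant therapy". This stands too. At an assumed 5–10% with few variables selected, the loss is much smaller. The protocol, however, gives no higher figure, while missing data and effective prophylaxis both lower the count.

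**Some models would survive.** A reader might infer that any model from these data would keep little of the real signal. That is too strong. With attainable AUC 0.85 and 16 cases, the best-five model still reaches about 0.77 and the all-70 model 0.71. The protocol states no expected AUC, so neither the weak-signal nor the strong-signal setting can be taken as given.

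**The risk grouping uses a smaller model.** The four groups do not depend on a 70-indicator model, and the item 2a model is not condemned by this point. It is not yet a ready fixed score either: its list of factors is open-ended, and no weights or cut-off are stated.

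**The statistical analysis plan could deal with this.** It could set the modelling method. It cannot add cases, and both the sample-size argument and Objective 1 are in the protocol.

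**Conclusion.** Wrong as written. The only justification for 800 counts patients, and the protocol's own incidence turns 800 into about 6–16 PJP cases: 0.08–0.23 per indicator, about 4–14 cases after the stated missing data, and fewer if prophylaxis is effective. The rule does not show that 800 is enough for reliable development of a new PJP model or screening criteria from the 70 indicators.

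The case count rests only on the protocol's figures and on applying the Background incidence to this cohort. How much performance is lost rests on the illustration:

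- severe with weak signal or 6 cases (attainable AUC 0.75: about 0.56–0.62 in new patients with 6–16 cases);
- moderate with strong signal and 16 cases (attainable 0.85: about 0.71 with all 70, 0.77 with the best five);
- much smaller at an assumed 5–10% incidence with few variables selected.

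Nor does it follow that the study must enrol 3,500–10,000 patients. Those figures show the scale of the gap and are not a proposed sample size.

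**What to change.** Keep 800 as planned recruitment and delete the claim that the 10-per-dimension rule makes it sufficient. Replacement text could read:

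*Planned recruitment is 800 patients. About 6–16 PJP cases are expected at an incidence of 0.7–2%, fewer after missing data and if prophylaxis is effective; incidence in this treated cohort may differ. This number is not expected to support reliable development of a new model from 70 indicators.*

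In Objective 1 and the Background:

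- Label the machine learning on the 70 indicators exploratory, with performance corrected for optimism.
- Limit any main model to a few pre-specified predictors. The Study process 2a model is one candidate, provided its factors, weights and cut-off are fixed before PJP outcomes are seen.
- If precision is quoted, use intervals that stay within 0–1, such as the logit-scale ones above.
- If the old calculation is kept anywhere, correct 70 × 1.2 × 10 to 840.

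The cost is protocol wording only, with no extra patients. The downside is a more modest modelling objective and a less favourable stated figure.

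### The sample-size line does not give 800: its product is 840, and multiplying by 1.2 does not offset 20% missing data, so 800 meets the protocol's own rule only up to about 11–12% missing

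*Protocol*

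**What the plan says.** Everything needed is in one paragraph of the protocol, under Sample size estimation.

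- Total: "It is expected to prospectively collect a total of 800 patients diagnosed with AIIRD in our hospital".
- Rule, taken from a web page: "which is about 10 times the number of dimensions + 1".
- Number of dimensions: "Prospective data expected into the analysis of the parameters/index for 70".
- Allowance: "Considering that about 10-20% of patients may have missing data in real-world practice, the final sample size".
- Result, continuing that sentence: "for prospective collection was $70*1.2*10 \approx 800" (the code before 800 is the approximately-equal sign).

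The factor 1.2 corresponds to the upper end, 20%, of the stated missing-data range. No reason is given for going from the product to 800. The paragraph does not say whether patients with missing data leave the model or are imputed.

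**The concern.** This line is the protocol's only numerical support for 800, and it serves the first objective, developing and validating the prediction model. Two steps in it fail. The three numbers do not multiply to the result, and a required minimum has been rounded down. The inflation for missing data also uses the wrong operation: adding 20% to a target and then losing 20% of the larger number does not return to the target. Both slips push the figure down. At the upper end of the missing-data range that the protocol itself expects, the planned enrolment would leave fewer complete records than its own rule asks for.

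**Working it through.** **Inputs (all from Sample size estimation).** Parameters p = 70; rule of about 10 × dimensions + 1; missing share m = 10% to 20%; planned total 800. The web page behind the rule is not available, so the rule is taken as the protocol words it. It can be read in two ways:

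- 10p + 1 = 701
- 10(p + 1) = 710

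The protocol's formula uses neither. It starts from 10p = 700.

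**1. The protocol's own figure.** 70 × 1.2 × 10 = 840. The stated 800 is 40 lower, and 40/840 = 4.8%.

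**2. The allowance for missing data.** To keep N usable records after losing a share m, enrolment must be N/(1 − m), rounded up.

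| Usable records needed | m = 10% | m = 15% | m = 20% | N × 1.2 |
|---|---|---|---|---|
| 700 | 778 | 824 | 875 | 840 |
| 701 | 779 | 825 | 877 | 842 |
| 710 | 789 | 836 | 888 | 852 |

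At 20% missing neither operation gives 800. Correcting the product alone would not be enough: 840 × 0.8 = 672, still below 700.

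**3. What 800 delivers if incomplete records are dropped.**

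| m | Complete records, 800(1 − m) | Per parameter (÷ 70) | Against 700 / 701 / 710 |
|---|---|---|---|
| 10% | 720 | 10.3 | met on all three |
| 15% | 680 | 9.7 | short by 20 / 21 / 30 |
| 20% | 640 | 9.1 | short by 60 / 61 / 70 |

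**4. The largest missing share that 800 can absorb.**

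- Base 700: 1 − 700/800 = 12.5%
- Base 701: 1 − 701/800 = 12.4%
- Base 710: 1 − 710/800 = 11.25%

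With the extra 1 included, the limit is about 11–12%, near the lower end of the 10–20% range.

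**5. The list length that 640 complete records match under the same rule.** (640 − 1)/10 = 63.9, so 63; and 640/10 − 1 = 63. Both readings give 63.

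**6. If nobody is dropped.** 800/70 = 11.4 per parameter, and 800 exceeds both 701 and 710. No shortfall then exists.

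**The case against.** The best defence is that the paragraph presents itself as approximate. The rule is followed only roughly, it is worded as about 10, and the result carries an approximately-equal sign. On that view, going from 840 to 800 is a 4.8% rounding, and 800 is a sensible figure for a lower missing share (778 to 789 at 10%). Part of this stands. The missing + 1 is worth 1 patient or 10 and falls within the word about, so it should not be counted as a separate error. The hedging does not rescue the inflation step, which would fall short at 20% even if 840 had been kept. Nor did the authors write a lower missing share; they wrote 1.2.

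A second defence is that the shortfall presumes a complete-case analysis. The protocol says only that patients may have missing data, and how these are handled may properly be left to a statistical analysis plan. This stands as a condition on the result. Inflating for missing data does imply that records are lost, but imputation would remove the shortfall.

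A reader might go further and infer that 800 patients cannot support the planned model. The documents do not support that. A shortfall of about 9% at one end of the range, against a rule of thumb worded as about 10, does not make a model fail. The protocol also does not say that one model keeps 70 terms. Those 70 are indices expected to enter the analysis, while Study process, item 2, describes a model that combines one existing immunoglobulin factor with a few recognised risk factors.

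The opposite inference, that a list of 63 to 71 parameters would be adequate once the arithmetic is right, is not supported either. The rule counts patients. If the 0.7% to 2% incidence in the Background applied to this cohort and its follow-up, 800 patients would yield 800 × 0.007 = 5.6 to 800 × 0.02 = 16 PJP cases. No change from 70 to 63 candidates matters much against so few.

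**Conclusion.** The point holds as an error in the written derivation. The product is 840, not 800, and a 20% loss needs division by 0.8, which gives 875 (877 to 888 with the + 1). These two statements are plain arithmetic and need no assumption.

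The shortfall is conditional. It arises only if patients with missing data are left out of the model, and only above about 11–12% missing. At 10% the rule is met; at 20% the plan is 60 to 70 complete records short. The size is moderate. It concerns the justification for the prediction-model objective and does not bear on the comparison of PJP incidence between the prophylaxis groups. It is worth correcting because it is the only stated basis for the sample size, anyone who multiplies the three numbers will see that they do not agree, and the correction needs no further patients.

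**What to change.** Keep 800 and rewrite the paragraph. Replace 70 × 1.2 × 10 with (10 × 70 + 1)/(1 − missing share), and state what 800 gives. For example:

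> Under the rule adopted here, 70 parameters call for 701 usable records, which means enrolling 779 patients at 10% missing data and 877 at 20%. The planned 800 patients give 720 to 640 complete records at 10% to 20% missing, or about 10.3 to 9.1 per parameter, and meet the rule up to about 12% missing.

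Then add one of two statements:

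- The candidate list is shortened to 63, which agrees with the rule at 20% missing: (10 × 63 + 1)/0.8 = 788.75, so 789, and on the other reading 10 × (63 + 1)/0.8 = 800.
- Missing values are imputed, so that all 800 patients stay in the model and no inflation is needed.

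Word either one as agreement with the protocol's own rule. Do not write that 800 patients support 63 to 71 parameters, because the rule takes no account of the number of PJP events.

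The cost is one paragraph of protocol wording and, under the first option, seven fewer candidate variables. No extra patients are needed.

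### PJP infection is listed among the events that end follow-up, although PJP-related mortality and the outcomes of PJP are to be studied

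*Protocol*

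**What the plan says.** Protocol, Study process, item 4 (Follow-up and data collection) opens with a general call for long-term follow-up with regular collection of clinical data. It then sets the schedule: "Study visits were set at baseline, 6 and 12 months after the initiation of treatment". Next it states that the "end points of follow-up were PJP infection, occurrence of serious side effects, death, loss to follow-up, end of follow-up, or withdrawal from the study". The sentence after that names PJP incidence as the main outcome and adds that "secondary indicators include TMP/SMZ related adverse events, PJP related mortality, other prognostic indicators and parameters of the respiratory system".

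Two earlier places set the aim. Objective 2 is to "Investigate the impact of prophylactic treatment on the incidence and outcomes of PJP in AIIRD patients", and the Study design section says that "the impact of prophylactic anti-PJP treatment on incidence and outcomes will be explored". The Background gives the clinical reason: "AIIRD patients with PJP are prone to progress to respiratory failure, with severe symptoms, poor prognosis and high mortality". It also quotes a PJP incidence of 0.7% to 2% in this population, without a time frame.

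On grouping, Study process, item 3(a) says of the patients that "they are further divided into 4 groups according to the intention-to-treat principle".

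**The concern.** The list of end points of follow-up contains loss to follow-up, withdrawal and the end of follow-up itself. None of these is an outcome, and the outcomes are named separately in the following sentence. The natural reading is therefore a list of events at which observation of a patient stops. PJP infection is on it.

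A PJP-related death normally comes after the diagnosis of PJP, as do respiratory failure and the rest of the prognosis. If observation stops at diagnosis, such a death is recorded only when PJP is first recognised at or after death. One secondary indicator and the outcomes half of Objective 2 would then have almost no data. A statistical analysis plan can define censoring, but it cannot supply data that were never collected, so this belongs in the protocol.

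Serious side effects are on the same list. Ending observation there leaves any later PJP in those patients uncounted, which sits poorly with groups formed by intention to treat.

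**Working it through.** **The passages side by side**

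| Place in the protocol | What it requires |
|---|---|
| Study process, item 4, list of end points | Follow-up ends at PJP infection, serious side effect, death, loss, end of follow-up or withdrawal |
| Study process, item 4, next sentence | PJP-related mortality, prognosis and respiratory parameters as secondary indicators |
| Objectives, item 2; Study design | Effect of prophylaxis on the outcomes of PJP, not on incidence alone |
| Study process, item 4(a), opening sentence and visit schedule | General long-term follow-up with visits at baseline, 6 and 12 months; silent on PJP cases |

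The first row closes observation where the second and third need it to continue. The fourth does not settle the matter: it does not say that PJP cases stay in follow-up, and the list in the same section bounds it.

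**What is affected and what is not**

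- PJP incidence: not affected by PJP ending follow-up, because the event has been recorded by then.
- Adverse events related to trimethoprim-sulfamethoxazole (TMP/SMZ): still collected up to the end of follow-up.
- Prognostic and respiratory indicators: still collected in patients without PJP; only the values after PJP are at risk.
- PJP-related mortality: almost wholly at risk.

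**Size**

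Inputs: 800 patients (Sample size estimation); incidence 0.7% to 2% (Background). Assumptions: this incidence is a 12-month risk without prophylaxis, and case fatality is 10% to 50%. The protocol gives no fatality figure beyond calling mortality high.

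- Expected PJP cases = N × risk: 800 × 0.007 = 5.6; 800 × 0.02 = 16.
- Binomial 2.5% to 97.5% range: 2 to 11 cases at 0.7%; 9 to 24 at 2%.
- Expected deaths = cases × fatality: at 0.7%, 5.6 × 0.1 = 0.56 to 5.6 × 0.5 = 2.8; at 2%, 16 × 0.1 = 1.6 to 16 × 0.5 = 8.

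The case counts are expectations, not maxima, and fewer are expected if prophylaxis works. The protocol's expression for its sample size, 70 × 1.2 × 10, gives 840 rather than 800. With 840 the expected cases are 840 × 0.007 = 5.9 and 840 × 0.02 = 16.8, so nothing here depends on that difference.

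No comparable calculation is offered for serious side effects, because the protocol gives no rate for them.

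**The case against.** The strongest reply is that the list is loosely worded and is really an event-or-censoring list for the primary outcome. It is circular in naming the end of follow-up as an end point of follow-up, and it mixes clinical events with reasons for censoring. The next sentence names PJP-related mortality, and the Background plans to relate early indicators to PJP infection and its outcomes. On this view time at risk ends at PJP, while item 4(a) and the scheduled visits keep collecting data. The study is also run in one hospital, and nothing forbids recording the course of a PJP case.

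This reading is plausible, and it limits the claim. A reader might infer that data collection will certainly cease at PJP; the document does not establish that, so the loss of data is conditional on the literal reading. But the milder reading is nowhere stated, and no visit or vital-status check after PJP is described.

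It is also fair to say that so few deaths could not support a precise comparison between groups even with complete follow-up. That makes the outcome descriptive. With so few cases, the course of each one still matters for the description.

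On serious side effects, the reply is that intention to treat is invoked for forming the groups, not for follow-up, and that the section on risks asks for regular follow-up of symptoms and signs. Both are true. Neither says that PJP is still recorded after such an event.

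**Conclusion.** The conflict is real and should be resolved in the protocol. As worded, follow-up ends at PJP, while a secondary indicator and part of Objective 2 need observation after it. If the list was meant only to end time at risk for the primary outcome, that has to be written down.

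The stake is modest: about 6 to 16 PJP cases and about 0.6 to 8 PJP-related deaths, resting on the assumed 12-month risk without prophylaxis and the assumed 10% to 50% fatality.

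Three stronger conclusions might be drawn, and the document does not support them:

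- That the primary outcome is compromised by PJP ending follow-up. It is not.
- That leaving at a serious side effect biases the comparison of PJP incidence in a known direction or by a known amount. Without event rates, neither can be stated; the point is only that later PJP would go uncounted.
- That stopping TMP/SMZ ends follow-up. It is not on the list.

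**What to change.** Reconcile the passages by separating two things in Study process, item 4:

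1. State that PJP infection ends time at risk for the primary outcome only. Vital status, prognosis and respiratory parameters of PJP cases are still collected at the month-6 and month-12 visits.
2. State that PJP and vital status are still recorded at those visits after a serious side effect.
3. State that data collection ends before month 12 only for death, loss to follow-up or withdrawal.

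This concerns data collection alone and changes nothing in treatment. The cost is one or two sentences of protocol text and at most one or two already scheduled contacts per affected patient: two if the event falls before month 6, one if it falls later, and fewer if the patient dies.
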